The primary purpose of this randomized controlled trial is to determine if patient self-matching to psychotherapy treatment methods improves 1) drinking outcome, 2) compliance and 3) quality of life for patients being treated for alcohol problems compared to assignment as usual, which is by the means of expert matching.

A priori hypotheses

1. Patients who choose their own treatment will show significantly greater reductions in alcohol consumption (measured by number of days with excessive drinking) at follow-up, when compared to patients assigned to treatment by expert match.
2. Patients who choose their own treatment method will show significantly better compliance in treatment (measured by retention) when compared to patients assigned to a specific treatment method by expert match.

Material and methods

Study Design

The study is conducted as a superiority randomized controlled trial. 401 consecutive patients aged 18 or more are enrolled. All new patients fulfilling the inclusion criteria receive oral and written information about the study. Patients are randomized to either expert matching (algorithm) or self-matching. See the study protocol for more information on referral routines[13].

Study procedures

Information about the study is presented when the potential participant first attends the treatment center. If the patient needs treatment for withdrawal symptoms, the information is not given until those symptoms are sufficiently treated.

The baseline interview is divided into two sessions to avoid fatigue during a long assessment. This is already standard procedure in the clinic for everyone receiving treatment regardless of participation in this study. Upon written and oral

consent patients are randomized to either choosing their own treatment among five options or being assigned to one of these options by means of an algorithm[14] and expert opinion. Patients participating in the study will be re-interviewed 6 months after initiation of treatment.

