Getting patients to participate in studies and getting a high follow-up rate is usually an obstacle in research, thus we have designed the study routines as similar as possible to the usual assessment routines in the participating treatment institution. The only difference for those participating in this study is the 45-minute follow-up interview. To ensure a high follow-up rate we collect phone number, e-mail and home address on patients and their next of kin. If patients decide to be anonymous, we underline the importance of their responsibility to contact the treatment center 6 months after treatment start.

Randomization and blinding

Patients are assigned to conditions by REDCap (Research Electronic Data Capture) from Open (Odense Patient Data Explorative Network), a computer-based randomization system. The interviewer in charge of the first baseline interview will activate the randomization, when the patient has agreed to participate in the study. The patient witness' the randomization and the result are revealed immediately.

A case report for each participant will be prepared and labeled with participant number. All case reports will be stored in a locked storage inaccessible to the therapists, who are to remain uninformed of how patients were assigned to treatment. Patients are urged not to reveal their group assignment.

Data

The following instruments will be administered to provide standardized measures of alcohol problems, quality of life and personality traits:

- Addiction Severity Index (ASI) is an assessment tool for addiction problems [15].
- Time Line Follow Back (TLFB) is an assessment tool for measuring drinking days the last 30 days [16].
- WHO quality of life 26-item questionnaire (WHOQOL-BREF) [17].

- NEO Five-Factor inventory-3 (NEO-FFI-3) is a tool for measuring personality traits [18].
- Personal Happiness Form (PHF) is a tool for assessing well-being [19].

These validated and widely-used instruments will allow direct comparisons with mainstream clinical trials.

Statistical analyses and sample size

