A multiple regression model will be used to model percent of days with drinking/excessive drinking. If the model validation shows that Gaussian multiple regression does not fit due to severely non-normal data, a multiple quantile regression model will be used instead. Both modeling approaches allow for inclusion of additional explanatory variables. A two-sided alternative will be used with a significance level of $p=0.05$. We expect that proportion of patients assigned to the five treatments will differ between the two groups; hence, type of treatment, sociodemographic data and problem severity will be integrated in the analysis as explanatory variables.

Power calculation

To our knowledge no similar experimental studies have been conducted. The power calculation is therefore estimated from what clinicians' regard to be a clinically meaningful difference in outcome. A study by Miller and Manuel [20] found that clinicians estimated the difference between two treatment methods to be meaningful for implementation in daily practice if the continuous outcome measures (e. g. number of days with excessive drinking) were halved. The power calculation is based on the number of days with excessive alcohol abuse over the last 30 days after 6 months of treatment.

Currently, patients at the participating outpatient clinic drink on average excessively 5.7 days ($SD=9.7$) over the last 30 days after 12 months of treatment. With the new methods for assigning treatment to patients, we seek to halve the number of days with excessive drinking to an average of $5.7/2 = 2.85$ days, i.e. a reduction of 2.85 days. We assume the standard deviation will be the same for the reduced number of days. Most likely, it will be smaller since less than zero days of excessive drinking is impossible, i.e. the method is conservative. As stated by Miller & Manuel [20] this power calculation is based on practitioners' judgment of a meaningful difference in outcome, rather than statistical significance based on other studies. By this approach, a total sample of 200 patients in each group is needed to have 90% power of detection a difference of this magnitude using a 0.05% level of statistical significance (Figure 2).

Sensitivity analyses

Complete case and worst-case computation will be carried out.

Interim analyses and stopping rule

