An Independent Data Monitoring Board was assigned to carry out interim analyses. In case of significant and clinically relevant difference the study will be terminated due to ethical responsibility to provide the best treatment possible.

Start of data analyses

Data analyses will start primo January 2020.

Level of confidence and *p* values

A confidence level of 95% and *p* value of 0.05 is assigned.

Missing data

Incomplete follow-up data are assumed to be missing at random (MAR) and will be addressed by the MICE (multivariate imputation by chained equations) method of multiple multivariate imputation. Appropriate auxiliary variables will be included in the imputation model, the resulting datasets will be analyzed separately, and results will be combined using the rules of Rubin.

Outcome measures

For each outcome measure, two analyses will be carried out:

1. Intention-to-treat analyses (ITT) will be carried out on all patients, irrespective of whether they completed the interventions or were re-interviewed. Regarding incomplete data, multiple imputations is used together with ITT but there will be some caveats.
2. Completer (on-treatment) analyses will be carried out on patients who completed the respective interventions.

Results will be published regardless of our findings.

Primary outcome:

Number of excessive drinking days 6 months after initiation of treatment.

Secondary Outcomes:

1. Compliance measured by retention. At 6 months follow up the number of sessions attended is measured.

2. The four dimensions of Quality of life as measured by WHOQOL.

Table 1. Demographics and baseline data.

	Self-Match	Expert match (TAU)	Significance level
Demographics			
Current age mean (SD)			
Male			
Currently cohabiting or married			
Full or part time employment			
Annual income Mean (SD)			
Education (>high school)			
Treatment related to AUD and substance use			
Previously received AUD treatment			
Previously received SUD treatment			
Currently suffering from SUD			
Use of alcohol			
Number of heavy drinking days last 30 days			
Number of drinking days last 30 days			
Overall amount of alcohol consumption last 30 days			
Quality of Life			
Physical domain (sum score)			
Psychological domain (sum score)			
Social domain (sum score)			
Environment domain (sum score)			

Table 2. Follow up data

	Self-Match group	Control Group	Significance level
Follow up rate			
Percentage completed follow up			
Drinking outcome			
Heavy drinking days last 30 days			

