Number of drinking days last 30 days			
Overall alcohol consumption last 30 days			
Retention			
Compliance (drop out)			
Average number of sessions completed			
Quality of Life			

Physical domain (sum score)
Psychological domain (sum score)
Social domain (sum score)
Environment domain (sum score)

Table 3: Treatment success of selfmatch compared to expert match. Treatment success defined as 50% reduction in heavy drinking days.

	Heavy drinking days		Number of drinking days		Overall consumption		Compliance (drop out)		Number of sessions completed		QoL physical domain		QoL psychological domain		QoL social domain		QoL environment domain	
	OR	CI	β	CI	β	CI	β	CI	β	CI	β	CI	β	CI	β	CI	β	CI
Expert-match																		
Self-match																		
Intercept																		

Trial status

The second version of the protocol was accepted the 17th of November 2016. The study was accepted by the Regional Scientific Ethical Committee for Southern Denmark the 24th of March 2017. Recruitment began 22nd of May 2017 ended the 5th of April 2019.

Trial registration: ClinicalTrial.gov identifier: NCT03278821

Declarations

Ethics approval and consent to participate

The Study was presented for the Regional Scientific Ethical Committee for Southern Denmark, who decided that the study did not need formal approval from the committee. Reference number: S-20170027. All procedures in the study are in accordance with the second Declaration of Helsinki.

Both oral and written information will be given to patients by the person who undertakes first baseline interview. Patients must sign informed consent document if they want to participate in the study.

All appointments in Center for Alcohol Treatment Odense are situated in private rooms with quiet and calm atmosphere and there will be no interruptions.

Availability of data and materials

All data collected in the study will be treated and stored strictly confidentially in REDCAP, OPEN. The datasets generated and/or analyzed during the current study are available from the corresponding author on reasonable request.

Competing interests

[name] (PI), [name] and [name] are employees of the University of Southern Denmark and Region of Southern Denmark. [name] is employed at the psychiatry of Region Syddanmark. None of researchers have competing interests to declare.

Funding

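### The drinking-outcome model adjusts for type of treatment, which is set after randomisation by the mechanism under test, so its arm coefficient need not be the effect of self-matching

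*SAP*

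**What the plan says.** Under Study procedures, consenting patients are "randomized to either choosing their own treatment among five options or being assigned to one of these options by means of an algorithm" together with expert opinion. Randomization and blinding gives the timing: "The interviewer in charge of the first baseline interview will activate the randomization, when the patient has agreed to participate in the study". The patient sees the result at once.

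The first a priori hypothesis is that "Patients who choose their own treatment will show significantly greater reductions in alcohol consumption" than patients matched by experts. Outcome measures adds: "Intention-to-treat analyses (ITT) will be carried out on all patients, irrespective of whether they completed the interventions or were re-interviewed".

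The model is in Statistical analyses and sample size: "A multiple regression model will be used to model percent of days with drinking/excessive drinking", with quantile regression as the fallback. The choice of covariates starts from an expectation about the arms: "We expect that proportion of patients assigned to the five treatments will differ between the two groups". The SAP draws its covariate set from that expectation: "hence, type of treatment, sociodemographic data and problem severity will be integrated in the analysis as explanatory variables".

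The SAP states no direct-effect estimand. Its sensitivity analyses are a complete-case and a worst-case analysis; neither drops type of treatment. Table 3 ("Treatment success of selfmatch compared to expert match") has rows for the two arms and the intercept and names no covariates.

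**The concern.** A covariate adjustment keeps the protection of randomisation when the covariate is fixed before allocation. Type of treatment is fixed afterwards, by the very process being compared. The SAP's reason for adjusting, a different mix in the two arms, is therefore not a baseline imbalance. It is one of the ways in which self-matching could work.

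Two things follow.

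- **Lost effect.** Any benefit that arises because patients choose treatments that are better on average is taken out of the arm coefficient. Benefit from individual fit is not removed in general.
- **Lost comparability.** Within one treatment, the model compares patients who chose it with patients to whom it was assigned. These groups may differ in prognosis. Where the covariates do not capture the difference, the arm coefficient is biased.

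At stake is the answer to hypothesis 1: the model could miss a real overall benefit or report one that does not exist.

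**Working it through.** Differences are self-match minus expert match in excessive drinking days out of 30; negative favours self-matching. From the SAP: 200 per arm, SD 9.7, target 2.85 days, two-sided 0.05. Treatment shares, treatment effects and links between allocation and prognosis are not given, so those below are assumptions.

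**1. The plan's own figure.** SE = 9.7 × √(2/200) = 0.97, and 2.85/0.97 = 2.94. Power is Φ(2.94 − 1.96), about 83.6% (83.4% by t-test), against the stated 90%. The 200 per group is reproduced only with a one-sided 0.05 test (199). That mismatch is a separate matter; 83% is the starting power here. The 2.85 days is framed as the gain from a new way of assigning treatment, so it is a total effect.

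**2. Identity.** In a linear model without arm-by-type interaction:

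total effect = direct effect + Σ (share in self-match − share in expert match) × (mean effect of that type).

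With type in the model, and no unmeasured common cause of type and drinking, the arm coefficient estimates the direct effect only.

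**3. Benefit only through the mix.** Assumed shares, best to worst treatment, self-match vs expert match:

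- mild: 25/20/20/20/15% vs 15/20/20/20/25%
- strong: 40/20/15/15/10% vs 10/15/15/20/40%

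With equally spaced effects and a 2-day gap (−1, −0.5, 0, 0.5, 1):

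- mild: 0.10 × (−1) + (−0.10) × 1 = −0.20
- strong: 0.30 × (−1) + 0.05 × (−0.5) + (−0.05) × 0.5 + (−0.30) × 1 = −0.65

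A 6-day gap multiplies these by three: −0.60 and −1.95. In simulation (3,000 trials per scenario) the adjusted coefficient was 0.01 to 0.02 throughout. For the strong mix and gaps of 2, 4 and 6 days, the rejection rate without type was 0.10, 0.26 and 0.49; with type it was 0.05.

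**4. Total effect held at −2.85.** Assumed shares: 5/10/15/30/40% in self-match, 20% each in expert match. For type effects +2, +1, 0, −1, −2, the mix term is −0.30 − 0.10 + 0 − 0.10 − 0.40 = −0.90.

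| Type effects | Mix term | Type-adjusted coefficient |
|---|---|---|
| equal | 0 | −2.85 |
| +2 to −2 days | −0.90 | −1.95 |
| +4 to −4 days | −1.80 | −1.05 |

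A large simulation gave the same values, and −2.85 without type in each case. Adding an unmeasured trait that drives both choice and drinking, with equal type effects, moved the adjusted coefficient to −3.13, so it can also overstate.

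**5. No true effect, allocation related to unmeasured prognosis.** The expert allocation score is assumed to correlate with outcome through prognosis not in the model. The two values at 0.30 are for the two directions of the correlation.

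| Correlation | Mix | Bias (days) | Type I error |
|---|---|---|---|
| 0 | – | 0.01 | 0.048 |
| 0.09 | mild | +0.14 | 0.050 |
| 0.09 | strong | +0.39 | 0.068 |
| 0.30 | mild | +0.43 / −0.39 | 0.077 / 0.071 |
| 0.30 | strong | +1.28 / −1.27 | 0.234 / 0.220 |

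Without type in the model, type I error was 0.048 to 0.049 in all null scenarios.

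**6. Benefit only through individual fit.** Assume 5.7 days of benefit for a patient who gets the best option, and that 60% of self-match patients get it. The coefficient was −2.76 without type and −2.91 with it, so the benefit survives. If the popular options also fit more patients, it was −3.09 against −2.74, and power fell from 87% to 69%.

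**7. Collinearity alone.** R² of arm on type is 0.025 (mild) or 0.187 (strong). The variance inflation 1/(1 − R²) is 1.03 or 1.23, and power at 2.85 days falls from 83% to 82% or 75%.

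**The case against.** **Other analyses are implied.** Table 2 has a significance column for heavy drinking days by arm. Table 3 shows no treatment-type rows and reports an odds ratio, which the described regression cannot produce. Total-effect results may therefore be reported. This stands in part: the text describes only one drinking model, but the shells suggest more. They name no test, model or covariate set, however, so they do not override an explicit sentence on covariates.

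**Separating choice from treatment mix is a legitimate question.** True, but that is a direct effect. It has to be named, and it needs the absence of unmeasured common causes of treatment type and drinking, which the SAP does not discuss. The hypothesis, the intention-to-treat commitment and the power calculation all concern the arms overall.

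**The magnitudes are assumed.** This stands. With the mild mix, the lost effect is 0.2 to 0.6 days against a 2.85-day target. The largest errors need both the strong mix and a residual correlation of 0.30 after adjustment for severity and sociodemographics. The fit scenario assumes a benefit as large as the clinic mean of 5.7 days.

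**The figures apply to the linear mean model.** This also stands. A mean of 5.7 with SD 9.7 on a 0 to 30 scale suggests strong skew, so the quantile fallback is realistic, and no magnitude is offered for it. The objection to the covariate applies there too, because it is still set after randomisation.

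**Conclusion.** The concern holds: the covariate rule is wrong as written for the stated hypothesis. The described model gives the total effect only in special cases, such as treatments that are equally effective on average with allocation unrelated to unmeasured prognosis. The SAP establishes neither condition.

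The size and direction cannot be determined from the SAP. On the assumptions above, the consequences run from almost none to the loss of the whole effect or a type I error of 22-23%; the strong-mix results are illustrations, not predictions. The conclusion rests on the order of events and on the hypothesis, not on any one scenario. Adjusting for sociodemographics and problem severity is not at fault where these are measured before randomisation.

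**What to change.** - Make the primary intention-to-treat model for excessive drinking days arm plus covariates measured before randomisation: baseline excessive drinking days from the TLFB, problem severity and sociodemographics. Leave type of treatment out, in the quantile fallback as well.
- Check which measures qualify. Randomisation takes place at the first of two baseline sessions, so measures from the second may come after the patient knows the arm.
- State that this model decides hypothesis 1, and name its covariates under Table 3.
- Keep any treatment-adjusted model as exploratory, with its direct-effect estimand and assumptions stated.
- The SAP does not say whether the same covariates apply to compliance and quality of life. If they do, leave type of treatment out of those models too.

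The cost is SAP wording. No new data are needed.

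### The self-match SD of 9.7 cannot occur at a mean of 2.85 days on a 0–30 count; equal SDs are the safe direction, but the stated 90% power is not a floor

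*SAP*

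**What the plan says.** All of this is in the SAP under *Statistical analyses and sample size*, mostly in *Power calculation*.

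- **Outcome and scale:** "The power calculation is based on the number of days with excessive alcohol abuse over the last 30 days after 6 months of treatment". Each patient's value is a number of days out of 30. The *Data* section gives the same 30-day window for the instrument: "Time Line Follow Back (TLFB) is an assessment tool for measuring drinking days the last 30 days".
- **Expert-match (current practice) inputs:** patients at the clinic "drink on average excessively 5.7 days ($SD=9.7$) over the last 30 days after 12 months of treatment".
- **Self-match target:** the mean is to be halved "to an average of $5.7/2 = 2.85$ days, i.e. a reduction of 2.85 days".
- **Self-match SD:** "We assume the standard deviation will be the same for the reduced number of days".
- **The SAP's own qualification, in the next sentence:** "Most likely, it will be smaller since less than zero days of excessive drinking is impossible, i.e. the method is conservative".
- **Result claimed:** 200 patients in each group for 90% power.
- **Test:** "A two-sided alternative will be used with a significance level of $p=0.05". The power sentence prints the level as 0.05%. I read this as 0.05, the value given here and again under *Level of confidence and p values*.

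**The concern.** A variable confined to 0–30 has a largest possible SD at any given mean, and that ceiling falls as the mean moves toward zero. The pair used for the self-match arm (mean 2.85, SD 9.7) lies above the ceiling. The SAP notices that the lower boundary matters but stops at saying that a smaller SD is likely.

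What is at stake is how the stated power will be read. Calling the method conservative next to a figure of 90% invites the reader to take 90% as the least that 200 per group deliver. If the result is null, that figure will be used to judge what the trial could have detected. It should follow from the stated inputs, or at least hold for every SD that the scale allows.

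**Working it through.** **Inputs (all from the SAP).** Expert-match mean 5.7 and SD 9.7; self-match mean 2.85 and SD 9.7; difference 2.85; 200 per group; two-sided 0.05; scale 0 to 30. No allowance for attrition is stated in the calculation, so none is used here.

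**1. The plan's own figure.** With a common SD of 9.7, the standard error of the difference is 9.7 × √(2/200) = 0.97, and the noncentrality is 2.85/0.97 = 2.94. Power from the noncentral t with 398 degrees of freedom:

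- two-sided 0.05: 83.4%
- one-sided 0.05: 90.1%

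By the normal approximation, n = 2 × 9.7² × (z_α + z_β)²/2.85² gives 244 per group for 90% power two-sided, and 199 one-sided. The stated 200 per group for 90% is thus reproduced one-sided but not with the two-sided test that the SAP specifies.

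**2. The ceiling on the SD.** For a variable on [0, 30] with mean m, the variance is at most m(30 − m).

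- m = 5.7: √(5.7 × 24.3) = √138.51 = 11.77. An SD of 9.7 is attainable.
- m = 2.85: √(2.85 × 27.15) = √77.38 = 8.80 (8.82 with the n − 1 divisor at n = 200). An SD of 9.7 is not attainable.

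The ceiling of 8.80 is reached only if 2.85/30 = 9.5% of patients drink excessively on all 30 days and everyone else on none. Solving m(30 − m) = 9.7² gives m = 3.56, so an SD of 9.7 needs a mean of at least 3.56 days.

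**3. Power at 200 per group with arm-specific SDs.** Two-sided 0.05, expert-match SD held at 9.7, unadjusted, complete follow-up; pooled SD = √((9.7² + s²)/2), where s is the self-match SD.

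| Self-match SD (s) | Basis | Pooled SD | Power |
|---|---|---|---|
| 9.7 | SAP's assumption (not attainable) | 9.70 | 83.4% |
| 8.80 | Ceiling at mean 2.85 | 9.26 | 86.7% |
| 7.25 | Assumption: same fraction of its ceiling as expert match, 9.7/11.77 × 8.80 | 8.56 | 91.3% |
| 4.85 | Assumption: every patient's days halved, 9.7/2 | 7.67 | 96.0% |

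Power of 90% is reached when s is about 7.7 or less. At the ceiling, the normal approximation gives 222 per group for 90% two-sided power, against 244 with equal SDs.

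**The case against.** The strongest reply is that the SAP already discloses the point. It says straight away that the SD will probably be smaller, gives the boundary at zero as the reason, and labels the choice conservative. That label is right about direction: every feasible self-match SD raises power at 200 per group and lowers the number needed. An SD above the attainable maximum is cautious by construction, and the power it gives is a valid lower bound so long as the expert-match SD is 9.7. All of this stands, and the remark about direction should stay in the SAP.

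It also stands that the gap between 83.4% and 90% does not come from the SD. It comes from the two-sided test; the SD assumption pushes power the other way. Nor is 7.25 or 4.85 given anywhere in the SAP. Both are illustrations, and the feasible results in the table, 86.7% to 96.0%, lie on both sides of 90%. Finally, the expert-match SD is itself an assumption: it is a 12-month clinic figure applied to a 6-month endpoint. If it were at its own ceiling of 11.77, with self-match at 8.80, power would be 78.1%.

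A reader might go further and infer that, because the planning scenario cannot occur, the sample size calculation is void or the trial too small on this account. The SAP does not support that: correcting the SD moves power up, from 83.4% to at least 86.7% with the expert-match SD at 9.7.

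The reply does not rescue the 90%. A conservative method should give a figure that the true power meets or exceeds. Under the SAP's two-sided test, 90% is above both what its own inputs give and what the ceiling gives.

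**Conclusion.** The self-match SD of 9.7 is unattainable at a mean of 2.85 on a 0–30 count; the limit is 8.80, so a smaller SD is certain. This follows from the SAP's own figures and needs no outside source. As a simplification it is safe in direction.

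The consequence is confined to the stated power. At two-sided 0.05 with 200 per group, 90% is not a floor: the floor is 83.4% under equal SDs, or 86.7% once the limit of the scale is applied, and 90% depends on a self-match SD of about 7.7 or less, a condition that the SAP does not state. These figures assume an expert-match SD of 9.7, a true difference of 2.85 days, an unadjusted comparison of means and complete follow-up.

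The point is minor. The SD assumption does not enter the planned regression, the imputation or the significance level.

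**What to change.** In *Power calculation*:

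1. Say that the 0–30 scale forces the self-match SD to 8.8 or below at a mean of 2.85 days, in place of saying that it will probably be smaller.
2. Keep the statement that the equal-SD assumption is conservative in direction.
3. Replace the 90% with the two-sided power for 200 per group: about 83% under the equal-SD simplification and about 87% at the feasible limit, given an expert-match SD of 9.7 and before attrition.
4. Show any higher figure only as a labelled assumption about the self-match SD, for example 91% at 7.25 or 96% at 4.85.

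The cost is a few sentences of wording. No patients or data are needed: the SAP reports 401 patients and recruitment closed on 5 April 2019. The downside is a slightly less favourable stated power, given as a range that depends on an assumed SD.

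### 200 per group gives about 83% power, not 90%, for the SAP's own two-sided 0.05 test with a common SD of 9.7

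*SAP*

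**What the plan says.** The SAP section on statistical analyses and sample size sets the test: "A two-sided alternative will be used with a significance level of" 0.05. The section on level of confidence and *p* values repeats this: "A confidence level of 95% and *p* value of 0.05 is assigned".

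The Power calculation subsection takes 5.7 excessive drinking days in the last 30 (SD 9.7) as the current clinic figure and seeks to halve it to 2.85. For the spread in the self-match group it says: "We assume the standard deviation will be the same for the reduced number of days". It adds that the SD will probably be smaller, and so calls the method conservative. It concludes that "a total sample of 200 patients in each group is needed to have 90% power of detection a difference of this magnitude". The end of that sentence prints the significance level as 0.05% and refers to Figure 2, which is not shown in the copy reviewed.

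The calculation mentions no loss to follow-up and no gain from covariates. The planned model does adjust: "sociodemographic data and problem severity will be integrated in the analysis as explanatory variables".

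**The concern.** The subsection gives every input that a two-sample power calculation needs, so the 90% can be checked directly, and with a two-sided test it does not follow. The SAP also presents the figure as cautious, because it treats the equal-SD assumption as conservative. A reader would therefore take 90% as a lower value with some margin above it, when the equal-SD calculation itself falls short.

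The sample size is no longer at stake. What remains is interpretation. If the result is non-significant, a reader who relies on the SAP will put the chance of missing a true 2.85-day difference at 10%. On the SAP's own inputs it is about 17% (100% − 83.4% = 16.6%).

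**Working it through.** **Inputs, all from the SAP.** Difference Δ = 5.7 − 2.85 = 2.85 days; common SD σ = 9.7; n = 200 per group; two-sided α = 0.05. The comparison is unadjusted with complete follow-up, since the calculation includes neither covariates nor loss. Power is taken from the noncentral t distribution (Welch form where the SDs differ).

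**Step 1: the plan's figure with the plan's test.**

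- Standard error = σ√(2/n) = 9.7 × √(2/200) = 0.97.
- Noncentrality = 2.85 / 0.97 = 2.938; standardized difference = 2.85 / 9.7 = 0.294.
- Two-sided 5% critical value on 398 degrees of freedom = 1.966.
- Power = **83.4%** (83.6% by the normal approximation). With the 401 patients enrolled, split 200/201, it is 83.5%.

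The 90% is not reproduced.

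**Step 2: what 90% would need, two-sided 0.05.**

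- Sample size at Δ = 2.85: 244.4, so 245 per group.
- Difference at 200 per group: about 3.15 days.

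**Step 3: which test fits the stated pair.**

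| Test, common SD 9.7 | Power at 200 per group | n per group for 90% |
|---|---|---|
| Two-sided 0.05 (as specified) | 83.4% | 245 |
| One-sided 0.05 | 90.1% | 200 (199.1 before rounding) |
| Two-sided 0.0005 (0.05% read literally) | 28.6% | 528 (527.5 before rounding) |

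One-sided 5% matches both 200 and 90%. The SAP names no one-sided test, so this is a likely origin and not an established one. The printed 0.05% is evidently a misprint of 5% and does not explain the figure either.

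**Step 4: the smaller-SD remark.** On a 0 to 30 day scale with mean 2.85, the SD cannot exceed √(2.85 × (30 − 2.85)) = √(2.85 × 27.15) = 8.80. With control SD 9.7 and self-match SD 8.80:

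- Standard error = √((9.7² + 8.80²)/200) = 0.926; noncentrality = 2.85 / 0.926 = 3.078.
- Power = **86.7%**.

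Other self-match SDs (assumed; the SAP gives none): 8.0 gives 89.2%, 7.5 gives 90.6%. The 90% is reached at about 7.7.

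**Step 5: factors left out of the calculation (assumed values, for scale only).**

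| Departure, two-sided 0.05 | SD 9.7 in both groups | SDs 9.7 and 8.80 |
|---|---|---|
| 10% loss (180 per group) | 79.4% | 82.9% |
| 20% loss (160 per group) | 74.5% | 78.4% |
| Covariate multiple correlation 0.30, no loss | 86.7% | not calculated |
| Covariate multiple correlation 0.43, no loss | 90.1% | not calculated |

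The loss rows ignore any information recovered by the planned multiple imputation. The covariate rows use a residual SD of 9.7 × √(1 − R²).

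**The case against.** The strongest objection is that a common SD of 9.7 cannot occur. At mean 2.85 the 30-day window caps the self-match SD at 8.80, and the SAP itself expects a smaller value. With control SD 9.7, no covariates and complete follow-up, the shortfall is then at most about 3 points, and it disappears if the self-match SD is about 7.7 or less. This stands as a limit on the size of the problem. It does not rescue the statement. The 90% is reported for equal SDs, with the smaller SD offered as extra margin, and the SAP commits to no smaller value.

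It is also fair that an unadjusted t-test figure is not the power of the planned analysis, which is a multiple regression with covariates, or quantile regression if the data are severely non-normal. Adjustment could restore 90%. But the SAP's calculation claims no such gain, so the correction has to be made on the basis the SAP used.

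The loss rates above are assumptions. The SAP's remark that "getting a high follow-up rate is usually an obstacle in research" is about research in general, and it goes on to describe steps to keep follow-up high. It shows that loss was in view but gives no expected rate.

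Finally, recruitment is over, and a confidence interval is a better guide to a null result than planned power. That lowers the consequence, but the figure stated in the SAP is still wrong.

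**Conclusion.** The concern holds. On the SAP's own inputs (200 per group, 2.85 days, SD 9.7 in both groups, two-sided 0.05, unadjusted, complete follow-up) power is 83.4%, about 7 points below the stated 90%. If the self-match SD is set to its largest possible value of 8.80, the gap is about 3 points. Covariate adjustment and a still smaller SD would narrow or close the gap, and loss to follow-up would widen it. None of these is part of the calculation, so none supports the 90%. The arithmetic is certain; that a one-sided test was used by mistake is an inference. This should be fixed, but it does not affect the validity of the planned analysis.

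**What to change.** Replace the power sentence with wording such as:

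> With 200 per group, a difference of 2.85 days and an assumed common SD of 9.7, power is about 83% at two-sided alpha 0.05, unadjusted and with complete follow-up (90% for a difference of about 3.15 days).

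If the smaller SD is kept as a remark, give about 87% for SDs of 9.7 and 8.80 under the same conditions. Do not present it as a general floor, since loss to follow-up would take power below it. Correct the printed 0.05% to 5%, and check that Figure 2 agrees with the restated figure.

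The cost is wording and a less favourable number. Recruitment ended on 5 April 2019, so the sample size, the test and the analysis sets stay as they are.
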